3.12. Stopping Rules and Discontinuation Criteria

There are no formal rules for early termination of this study. During the conduct of the study, serious adverse events will be reviewed (see Section 7.1.5) as they are reported from the investigational center to identify safety concerns. The study may be terminated by the sponsor at any time.

A patient may discontinue participation in the study at any time for any reason (eg, lack of efficacy, consent withdrawn, and adverse event). The investigator and/or sponsor can withdraw a patient from the study at any time for any reason (eg, protocol violation or deviation as defined in Section 11.1.2, noncompliance, or adverse event). In addition, patients with abnormal hepatic laboratory values (eg, ALT, AST, ALP, gamma-glutamyl transpeptidase [GGT], total bilirubin,

or international normalized ratio [INR]) may meet criteria for discontinuation from the study drug as summarized in [Appendix E](#).

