7.1. Adverse Events

7.1.1. Definition of an Adverse Event

An adverse event is any untoward medical occurrence in a patient administered a pharmaceutical product, regardless of whether it has a causal relationship with this treatment.

In this study, any adverse event occurring after the clinical study patient has signed the informed consent form for this study should be recorded and reported as an adverse event.

An adverse event can, therefore, be any unfavorable and unintended physical sign, symptom, or laboratory parameter that develops or worsens in severity during the course of this study, or significant worsening of the disease under study or of any concurrent disease, whether or not considered related to the study drug. A new condition or the worsening of a pre-existing condition will be considered an adverse event. Stable chronic conditions (such as arthritis) that are present before study entry and do not worsen during this study will not be considered adverse events.

Accordingly, an adverse event can include any of the following:

- intercurrent illnesses
- physical injuries
- events possibly related to concomitant medication
- significant worsening (change in nature, severity, or frequency) of the disease under study or other pre-existing conditions (Note: A condition recorded as pre-existing that is intermittently symptomatic [eg, headache] and that occurs during this study should be recorded as an adverse event.)
- drug interactions
- events occurring during diagnostic procedures or during any follow-up period of this study
- laboratory or diagnostic test abnormalities that result in the withdrawal of the patient from the study, are associated with clinical signs and symptoms or a serious adverse event, or require medical treatment or further diagnostic work-up, or are considered by the investigator to be clinically significant (Note: Abnormal laboratory test results at the screening visit that preclude a patient from entering the study or receiving study drug are not considered adverse events.)
- all events of possible drug-induced liver injury with hyperbilirubinemia (defined as AST or ALT $\geq 3 \times$ the ULN, plus either total bilirubin $\geq 2 \times$ the ULN or INR > 1.5) or

Hy's Law events require immediate study treatment cessation and reporting as a serious adverse event. Refer to [Appendix E](#) for guidance regarding monitoring patients with elevated liver function tests.

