7.1.6. Protocol-Defined Adverse Events of Special Interest

The following are considered protocol-defined adverse events to be sent to the sponsor's Global Patient Safety and Pharmacovigilance Department for evaluation: ophthalmic adverse events of at least moderate severity, events of possible drug-induced liver injury (AST or ALT $\geq 3 \times$ the

ULN, total bilirubin $\geq 2 \times$ the ULN or INR >1.5), Hy's Law events, or events of suspected anaphylaxis and severe hypersensitivity reactions. Severe hypersensitivity reactions will be monitored using the diagnostic criteria for anaphylaxis as outlined by the 2006 Joint National Institute of Allergy and Infectious Disease/Food Allergy and Anaphylaxis Network Second Symposium on Anaphylaxis (Sampson et al, 2006 [also see Appendix F]). In the event of suspected anaphylaxis, vital signs, including oxygen saturation and respiration rate, will be measured. Other assessments will be performed at the discretion of the investigator.

The process for reporting a protocol-defined adverse event is the same as that for reporting a serious adverse event (see Section 7.1.5.3). Protocol-defined adverse events for reporting to Pharmacovigilance Department can be either serious or nonserious according to the criteria outlined in Section 7.1.5.1.

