APPENDIX E. GUIDANCE ON SAFETY MONITORING

Guidance on Monitoring Patients with Elevated Liver Function Tests

Liver enzymes (ALT, AST, GGT, and ALP) as well as total and direct bilirubin will be measured (and indirect bilirubin will be calculated) at each study visit.

In any case of elevated ALT or AST to a level exceeding $\geq 2\times$ the ULN (including patients whose baseline ALT or AST levels are $\geq 2\times$ and $\leq 3\times$ the ULN, who may be enrolled in the study), a thorough medical history and physical examination with a focus on liver disease should be undertaken.¹ In addition, the patient should be instructed to refrain from alcoholic beverages.

In case of symptoms compatible with drug-induced liver injury during the study, patients will be instructed to return to the study center for an unscheduled visit or to go to the emergency room to measure liver enzymes as soon as possible. Solitary elevations of total or direct bilirubin, not accompanied by elevations of ALT or AST should be managed according to the discretion of the treating physician.

Elevation of Either ALT or AST to $\geq 3\times$ ULN

Confirmation is required prior to study drug discontinuation in cases of elevation of either ALT or AST $\geq 3\times$ ULN (Note: In cases of elevation of ALT or AST $\geq 8\times$ the ULN, no confirmation is required prior to study drug discontinuation, but the assessments below should be performed). The following procedures should be followed:

- The day in which the abnormal value is received from the laboratory will be considered as day 0.
- The investigator should repeat the test for confirmation purposes (this may be performed in a local laboratory along with complete blood count [CBC] and differential to assess for eosinophilia. In general, in case a blood sample is sent to a local laboratory, the following assessments [and reference ranges] are mandatory: ALT [serum glutamic pyruvic transaminase], AST [serum glutamic oxaloacetic transaminase], ALP, total and direct bilirubin, CBC [with differential for eosinophil count, separate tube], and INR [separate tube; not to be sent in a confirmatory test]). The investigator should also question the patient regarding symptoms.

The abnormality will be regarded as confirmed in each of the following scenarios:

- the baseline value was within the normal range and ALT or AST is still $\geq 3\times$ the ULN
- the baseline value was above the ULN and ALT or AST is $\geq 2\times$ the baseline value

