- Should the abnormality ($\geq 3\times$ the ULN in case baseline was within the normal range or $\geq 2\times$ the ULN in case the baseline value was above ULN but still $<5\times$ the ULN) persist further, the patient will be followed according to the investigator's discretion, but a blood sample for ALT, AST, GGT, ALP, and total and direct bilirubin should be sent to the central laboratory at least once a month.

ALT or AST $\geq 5\times$ but Less Than $8\times$ the ULN

In addition to the above procedures required for any elevation to levels $>3\times$ the ULN:

- Alanine aminotransferase, AST, GGT, ALP, total and direct bilirubin, CBC and differential count (to assess for eosinophilia), and INR should be monitored twice a week.
- At least for every other measurement, the tests should be sent to the central laboratory. The rest of the tests may be sent to a local laboratory. The INR should always be sent to a local laboratory.

ALT or AST $\geq 8\times$ the ULN

In addition to the above procedures required for any elevation to levels $>3\times$ the ULN:

- The study drug should be discontinued immediately, and the early withdrawal visit should be performed.
- For follow-up guidance, please see below section “Follow-Up of Liver Enzymes After Stopping Rules Are Met.”

Stopping Rules

In the following circumstances, the study drug will be discontinued immediately:

- any increase in ALT or AST to $\geq 3\times$ the ULN, combined with INR $>1.5\times$ the ULN or total bilirubin $>2\times$ the ULN
- any increase in ALT or AST to $\geq 3\times$ the ULN, which is accompanied by symptoms clearly associated with impaired liver function (eg, vomiting, nausea, fever, rash, eosinophilia) and not deemed related to other diseases (eg, vomiting or nausea triggered by migraine)
- any increase in ALT or AST to levels ≥ 5 but $<8\times$ the ULN, which is persistent for ≥ 2 weeks of repeated measurements
- any increase in ALT or AST to levels $\geq 8\times$ the ULN
- in any case where monitoring of liver enzymes cannot be performed according to the protocol guidance

Follow-Up of Liver Enzymes After Stopping Rules Are Met

- A patient who meets the above criteria for discontinuation of the study drug should be invited to the site to return the study drug. Early withdrawal visit activities should be performed as soon as possible.
- Liver enzymes should be monitored until normalization or stabilization of the abnormality, according to the discretion of the investigator.

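### The combined liver stopping rule in Appendix E is narrower than the mandatory rule in Section 7.1.1, and Appendix E contradicts itself on whether a repeat test must come before stopping

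*Protocol*

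**What the plan says.** Section 7.1.1 of the protocol, in its list of what counts as an adverse event, defines possible drug-induced liver injury as AST or ALT of at least 3 × ULN "plus either total bilirubin $\geq 2 \times$ the ULN or INR > 1.5". It says that these and Hy's "Law events require immediate study treatment cessation and reporting as a serious adverse event". It then refers sites to Appendix E "for guidance regarding monitoring patients with elevated liver function tests".

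Section 3.12, which covers stopping and discontinuation, does not cite that rule. It says that patients with abnormal hepatic values "may meet criteria for discontinuation from the study drug as summarized in" Appendix E. The Stopping Rules there order immediate discontinuation in five situations:

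- ALT or AST ≥3 × ULN, "combined with INR $>1.5\times$ the ULN or total bilirubin $>2\times$ the ULN"
- ALT or AST ≥3 × ULN with symptoms of impaired liver function
- ALT or AST of 5 to <8 × ULN lasting at least two weeks
- ALT or AST ≥8 × ULN
- liver monitoring that cannot be carried out as the protocol requires

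Earlier in Appendix E the text reads "Confirmation is required prior to study drug discontinuation in cases of elevation of either ALT or AST" to 3 × ULN or more, and the only exemption is ≥8 × ULN. An elevation counts as confirmed if baseline was normal and the repeat is still ≥3 × ULN, or if baseline was above ULN and the repeat is at least twice baseline.

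Section 7.1.6 uses "total bilirubin $\geq 2 \times$ the ULN or INR >1.5" in its definition of events of special interest, and adds that "The process for reporting a protocol-defined adverse event is the same as that for reporting a serious adverse event". SAP Section 7.3 repeats those cut-offs.

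**The concern.** One clinical event carries two immediate-stop thresholds, and the appendix that sites are sent to for hepatic discontinuation holds the looser one. Within that appendix, one paragraph tells the site to confirm first and another tells it to stop at once. No text says which instruction prevails.

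Safety is the primary objective (Section 2.2.1), liver enzyme elevation is a named potential risk (Section 1.4.1.1), and there is no data monitoring committee (Section 3.8.3). At stake is whether every site takes the same decision for the same laboratory result, and whether a patient whom Section 7.1.1 takes off drug could receive another injection.

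**Working it through.** **1. Threshold comparison.** Let *u* be the INR ULN, with ALT or AST ≥3 × ULN throughout.

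- Section 7.1.1 stops if bilirubin ≥2 × ULN or INR >1.5.
- The combined limb of Appendix E stops if bilirubin >2 × ULN or INR >1.5 × *u*.

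Bilirubin >2 × ULN implies ≥2 × ULN. For *u* ≥1.0, INR >1.5*u* implies INR >1.5. So every patient meeting the Appendix E limb also meets Section 7.1.1, but not the reverse. The bilirubin difference is only the exact boundary, whatever the laboratory range. The INR difference is 1.5*u* − 1.5 = 1.5 × (*u* − 1.0). The documents give no INR ULN, so *u* is assumed:

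| Assumed INR ULN | Appendix E cut-off | Excess over 1.5 |
|---|---|---|
| 1.0 | 1.50 | 0 |
| 1.1 | 1.65 | 0.15 |
| 1.2 | 1.80 | 0.30 |
| 1.3 | 1.95 | 0.45 |

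Example: ALT 4 × ULN, bilirubin 1 × ULN, INR 1.6, *u* = 1.1, no symptoms. Section 7.1.1 stops the drug because 1.6 >1.5. Appendix E does not, because 1.6 <1.65. The other Appendix E limbs do not catch this patient.

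**2. Does the confirmation paragraph really reach the immediate stops?** Take the five limbs in turn. The persistence limb already needs repeated measurements, the ≥8 × ULN limb is exempt, and the last limb concerns failed monitoring. An isolated, asymptomatic elevation of 3 to <5 × ULN is not a stopping reason in Appendix E at all. A rule that demands confirmation before discontinuation at ≥3 × ULN therefore has little to govern except the combined and symptomatic limbs, and those are the two that say stop immediately. Both are in conflict for ALT or AST of 3 to <8 × ULN.

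**3. When does the conflict change dosing?** Site staff give injections about every 28 days (Section 5.1), so a repeat within days does not in itself add a dose. Dosing changes when the repeat fails confirmation. Let baseline be *b* × ULN with *b* >1. The repeat is still ≥3 × ULN but unconfirmed when 3 ≤ repeat <2*b*, which needs *b* >1.5.

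- *b* = 2: confirmation needs 2 × 2 = 4 × ULN, so a repeat of 3.5 × ULN is unconfirmed even with bilirubin at 3 × ULN.
- New patients are excluded above 1.5 × ULN at screening (Section 4.2.2). This route therefore concerns mainly rollover patients, who have no numeric enzyme limit (Section 4.2.1). Appendix E itself allows for baselines of 2 to 3 × ULN.
- With a normal baseline, a repeat below 3 × ULN is also unconfirmed, whereas Section 7.1.1 mentions no confirmation step.

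**4. Next injection after each scheduled laboratory visit.** Laboratory visits 2, 4, 6, 8, 10 and 12 are followed 28 days later by injections at visits 3, 5, 7, 9, 11 and 13. Visit 2 tests apply to new patients and to rollovers entering after more than 30 days. The next injection is active at 6 of 6 in the monthly arms and at 2 of 6 (visits 5 and 11) in the quarterly arm. Without visit 2, the counts are 5 of 5 and 2 of 5.

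**The case against.** The strongest reply is that both thresholds can be obeyed. Section 7.1.1 is mandatory and cites Appendix E only for monitoring. Appendix E is titled as guidance, never says its list is exhaustive, and never tells a site to keep dosing. Section 3.12 is worded permissively. A site following every section would stop the patient. This stands for the threshold difference, and it is why a reader who infers that the protocol instructs sites to continue treatment goes too far. It does not settle the second defect: confirming first and stopping immediately cannot both be done.

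Reading the stop as immediate once confirmed is possible, and Section 7.3 does speak of laboratory adverse events confirmed by repeat testing. But the Stopping Rules do not say so, and Section 7.1.1 attaches no such condition to its stop.

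Two further points stand. Section 7.1.6 sets a reporting trigger, not a stopping threshold; it shows which cut-offs the protocol uses elsewhere and no more. And the exclusion of INR from the confirmatory sample does not make confirmation impossible, as might be inferred, because confirmation depends on ALT or AST alone.

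Existing safeguards also count. These events go to the sponsor within 24 hours. Confirmed elevations are retested around days 5, 8, 14 and 28 at 3 to <5 × ULN, or twice weekly at 5 to <8 × ULN. As written, that follow-up starts after confirmation, so it helps least when the repeat fails.

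**Conclusion.** The point holds, as a minor one. The wording difference and the contradiction within Appendix E are certain. The practical size of the INR gap is not: it is zero at an INR ULN of 1.0, and up to 0.45 only if the ULN is as high as 1.3. The bilirubin gap is a single boundary value.

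The threshold gap mainly concerns asymptomatic patients with ALT or AST of 3 to <5 × ULN and INR above 1.5 but not above 1.5 × ULN. At 5 to <8 × ULN the two-week persistence rule would normally act before an injection 28 days later. The confirmation conflict matters mainly when the repeat fails the ALT/AST rule and dosing continues although Section 7.1.1 or the Stopping Rules require a stop. The documents do not allow a count of such patients; they are probably few.

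A reader might infer that waiting for a repeat is extra exposure in itself, or that the trial's liver results are compromised. The documents support neither. Nothing is dosed between visits, and no efficacy estimate or SAP laboratory summary uses this wording.

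**What to change.** Make two edits to Appendix E at the next protocol amendment.

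1. In the Stopping Rules, replace the combined limb with: *ALT or AST ≥3 × ULN plus either total bilirubin ≥2 × ULN or INR >1.5.*
2. In the confirmation paragraph, add: *The confirmation requirement does not apply when ALT or AST ≥3 × ULN is accompanied by total bilirubin ≥2 × ULN, INR >1.5, or symptoms meeting the Stopping Rules.*

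Both are needed. The first alone leaves the confirmation conflict in place, and an exemption limited to the combined criteria would leave the symptomatic stop unresolved.

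The edits add no tests and need no SAP change. The threshold edit stops only patients whom Section 7.1.1 already requires stopping. The cost is that a few more borderline patients will come off drug without a confirmatory test, some of whom might have had a transient elevation.

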APPENDIX F. CLINICAL CRITERIA FOR DIAGNOSING ANAPHYLAXIS

Anaphylaxis is highly likely when any 1 of the following 3 criteria are fulfilled:

- a. Acute onset of an illness (minutes to several hours) with involvement of the skin, mucosal tissue, or both (eg, generalized hives, pruritus or flushing, swollen lips-tongue-uvula) AND AT LEAST ONE OF THE FOLLOWING
 - Respiratory compromise (eg, dyspnea, wheeze-bronchospasm, stridor, reduced peak expiratory flow [PEF], hypoxemia)
 - Reduced blood pressure (BP) or associated symptoms of end-organ dysfunction (eg, hypotonia [collapse], syncope, incontinence)
- a. Two or more of the following that occur rapidly after exposure to a likely allergen for that subject (minutes to several hours):
 - Involvement of the skin-mucosal tissue (eg, generalized hives, itch-flush, swollen lips-tongue-uvula)
 - Respiratory compromise (eg, dyspnea, wheeze-bronchospasm, stridor, reduced PEF, hypoxemia)
 - Reduced BP or associated symptoms (eg, hypotonia [collapse], syncope, incontinence)
 - Persistent gastrointestinal symptoms (eg, crampy abdominal pain, vomiting)
- e. Reduced BP after exposure to known allergen for that subject (minutes to several hours):
 - Infants and children: low systolic BP (age specific) or greater than 30% decrease in systolic BP
 - Adults: systolic BP of less than 90 mm Hg or greater than 30% decrease from that person's baseline

Source: Modified from Sampson HA, Munoz-Furlong A, Campbell RL, Adkinson NF, Jr., Bock SA, Branum A, et al. Second symposium on the definition and management of anaphylaxis: summary report-Second National Institute of Allergy and Infectious Disease/Food Allergy and Anaphylaxis Network symposium.[reprint in *Ann Emerg Med* 2006 Apr;47(4):373-80; PMID:16546624]. *J Allergy Clin Immunol* 2006 Feb;117(2):391-7.

The Statistical Analysis Plan for study TV48125-CNS-30051 (study protocol with amendment 01 dated 06 April 2016) has been amended and reissued as follows:

Amendment number	Date	Summary of changes	Reason for amendment
01	06 April 2017	Section 3.3, the definition of FAS is changed to all patients in the ITT population who receive at least 1 dose of study drug and have at least 10 days of post baseline e-diary efficacy assessments.	Per review comments from the FDA
		Section 4.3, Germany is removed from Table 2, Israel and Finland are added.	Germany did not participate in the study. Israel and Finland enrolled patients.
		Section 4.5, the missing data handling rule is modified. The monthly efficacy variables will be prorated to 28 days if the patient has ≥ 10 days of e-diary data for the month. If a patient has < 10 days of e-diary data for a month, the monthly number of days/hours of efficacy variables will be considered as missing.	Per review comments from the FDA

PREFACE

This Statistical Analysis Plan (SAP) describes the planned analysis and reporting for TEVA Branded Pharmaceuticals Products Research and Development, Inc. Study TV48125-CNS-30051, (A Multicenter, Randomized, Double-Blind, Parallel-Group Study Evaluating the Long-Term Safety, Tolerability, and Efficacy of Subcutaneous Administration of TEV-48125 for the Preventive Treatment of Migraine) and was written in accordance with standard operating procedure GBP_RD_702 (Teva Pharmaceuticals Global Branded Product Research and Development SAP).

This Phase 3 study is being completed to evaluate the long-term safety, tolerability, and efficacy of subcutaneous (sc) administration of TEV-48125 in adult patients with chronic migraine (CM) or episodic migraine (EM).

The structure and content of this SAP provides sufficient detail to meet the requirements identified by the Food and Drug Administration and International Conference on Harmonisation (ICH) of Technical Requirements for Registration of Pharmaceuticals for Human Use: E9 Guidance on Statistical Principles in Clinical Trials. All work planned and reported for this SAP will follow internationally accepted guidelines, published by the American Statistical Association, and the Royal Statistical Society, for statistical practice.

The following documents were reviewed in preparation of this SAP:

- Clinical Study Protocol TV48125-CNS-30051 with Amendment 01
- case report forms (CRFs) for Study TV48125-CNS-30051
- ICH E9 Guidance on Statistical Principles for Clinical Trials
- ICH E3 Structure and Content of Clinical Study Reports (CSRs)

The reader of this SAP is encouraged to also read the clinical protocol for details on the conduct of this study, and the operational aspects of clinical assessments and timing for completing a patient in this study. When differences exist in descriptions or explanations provided in the protocol and this SAP, the SAP prevails; the discrepancies will be explained in the CSR.

1. STUDY OBJECTIVES

1.1. Primary Objectives

The primary objective of this study is to evaluate the long-term safety and tolerability of sc TEV-48125 in the preventive treatment of migraine.

1.2. Secondary Objectives

There are no secondary objectives.

1.3. Exploratory Objectives

The exploratory objectives of the study are as follows:

- to evaluate the efficacy of sc TEV-48125 in patients with migraine, as assessed by the reduction of the number of migraine days
- to evaluate the efficacy of sc TEV-48125 in patients with migraine, as assessed by the reduction in the number of headache days of at least moderate severity
- to evaluate the efficacy of sc TEV-48125 in patients with migraine, as assessed by the reduction in the number of migraine days in patients not receiving concomitant migraine preventive medications at baseline
- to evaluate the efficacy of sc TEV-48125 in patients with migraine, as assessed by the reduction in the number of headache days of at least moderate severity in patients not receiving concomitant migraine preventive medications at baseline
- to evaluate the efficacy of sc TEV-48125 in patients with migraine, as assessed by the reduction in the number of migraine days for new patients and placebo-treated rollover patients
- to evaluate the efficacy of sc TEV-48125 in patients with migraine, as assessed by the reduction in the number of headache days of at least moderate severity for new patients and placebo-treated rollover patients
- to evaluate the efficacy of sc TEV-48125 in patients with migraine, as assessed by the reduction of the number of headache days of any severity
- to evaluate the efficacy of sc TEV-48125 in patients with migraine, as assessed by the reduction of the use of any acute headache medications
- to evaluate the efficacy of sc TEV-48125 in patients with migraine, as assessed by the discontinuation of use of concomitant preventive medications
- to evaluate the efficacy of sc TEV-48125 in patients with migraine, as assessed by the reduction of migraine-related disability and change in quality of life
- to evaluate the immunogenicity of TEV-48125 and the impact of antidrug antibodies (ADAs) on clinical outcome in patients exposed to sc TEV-48125
- to explore the correlation between pharmacokinetic parameters and drug efficacy

- to explore the relationship between genetic polymorphisms within the calcitonin gene-related peptide receptor-ligand complex (eg, CALCA, CALCB, CALCRL, CRCP, and RAMP) and migraine-associated genes (eg, PRDM16, AJAP1, TSPAN2, MEF2D, TRPM8, TGFBR2, PHACTR1, FHL5, C7orf10, MMP16, ASTN2, LRP1, APOA1BP, TBC1D7, FUT9, STAT6, ATP5B, and MTHFR) and mode-of-action-related pathways versus hypertension, migraine severity, and safety and efficacy responses
- to explore the relationship between biofluid bone, angiogenic, and inflammatory biomarkers with TEV-48125 concentrations and efficacy responses

